**10.0 Data and Specimen Banking**

We will not be collecting any data or specimen that will need banking for this study.

**11.0 Data Management\* and Confidentiality**

*11.1 Data analysis plan, including any statistical procedures.*

Data will be downloaded from REDCap into the Stata statistical package. For Aims 1 and 2 (feasibility, acceptability, and immediate impact), descriptive statistics will be used to report proportion of phone session completion and mean scores on exercise ratings.

To compare mean scores on outcome variables for Aim 3, paired t tests will be used to explore mean differences between baseline and follow-up values. All statistical tests will be two-tailed and  $p < .05$  considered significant, though this study will not be powered to detect statistically significant differences between baseline and follow-up points. Given the sample size and potential for drop-out, we will also consider alternatives to a t-test such as non-parametric tests, effect size calculations to support feasibility of study assessment procedures.

*11.2 Power analysis.*

This exploratory proof-of-concept study with 25 patients (anticipated 10 patients to complete the study), as noted, will not be powered to detect statistically significant differences between baseline and follow-up points, and is designed to assess feasibility of methods.

*11.3 Data Security Plan.*

All source data (e.g., chart review data and participant self-report) will be entered into the REDCap database. The PI ([name]) will review this data to ensure that it is being entered correctly and will perform 'test downloads' of the data to ensure that it can be captured in the statistical package to be used in this study. We will also use

**PROTOCOL TITLE: Development of a positive psychology intervention to improve mood and health related quality of life in patients post hematopoietic stem cell transplantation- Proof of Concept Trial**

locked cabinets/offices and password-protected databases to store personal information. Only study staff (currently just the PI) will have any access to personally identifiable information about participants, and such access will be limited only to information necessary to complete study tasks.

We will ensure that contact with participants is confidential by using only the phone numbers and other contact information that are specifically allowed by the participants and not leaving study-related messages for participants unless expressly allowed by participants. Upon enrollment, we ask all participants if it is acceptable to leave voice messages on their phones, as well as the appropriate times to call them. We adhere to all patient requests regarding contact.

*11.4 Quality Control.*

Safety monitoring will be performed by [name] (PI), who will ensure that the study team is adequately identifying, reviewing, and reporting adverse events and unanticipated problems to the Institutional Review Board (IRB). A more detailed description of monitoring mechanisms, intervals, and the information monitored is outlined below.

**Monitoring mechanism:** [name] (PI) will take primary responsibility for the data safety monitoring. However, this study will have a formal data safety monitoring board (DSMB), which will be chaired by [name] (psychiatry, primary mentor), and populated by [name] (psychiatry, peer-mentor), and [name] (psychologist, external to study).

**Monitoring intervals:** Monitoring of adverse events will occur on an ongoing basis with notification of [name] with any adverse study-related events. More systematic weekly meetings for review of feasibility/acceptability information and minor IRB deviations will be held between [name] and [name]. [name] will then discuss any potential issues regarding data safety or protocol deviations with [name] during weekly supervision meetings. This allows the team to review this information and adjust procedures as required. Furthermore, monthly journal clubs are held with the study team; these include discussions of related projects (e.g., studies of physical activity in cardiac patients, studies of positive psychological interventions). Finally, the formal DSMB will meet every four months to monitor patient safety outcomes. These ongoing, weekly, and intermittent reviews ensure that the study procedures minimize research-related risk by reviewing specific

**PROTOCOL TITLE: Development of a positive psychology intervention to improve mood and health related quality of life in patients post hematopoietic stem cell transplantation- Proof of Concept Trial**

outcomes linked to the project and by reviewing relevant literature to ensure that interventions are best practice.

**Information to be monitored:** Information to be monitored will include: (a) an evaluation of the progress of the research study, including assessments of data quality and timeliness and participant recruitment, accrual and retention consistent with plans for diversity and generalizability, (b) a review of study safety data—adverse event (and minor deviation) information—to determine whether the study should continue as originally designed, be changed, or be stopped, (c) review of procedures to maintain participant confidentiality (e.g., storage of identifiable information in locked cabinets, ensuring study databases have no personal identifying information, use of study participant numbers on communications about the study), and (d) an assessment of external factors or relevant information (e.g., developments in the literature, results of related studies, etc.) that may have an impact on the safety of participants or on the ethics of the research study, such as through the journal club listed above.

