### *1.2 Specific Aims/Objectives*

**Specific Aim #1 (Feasibility and Acceptability; primary aim):** To assess whether the novel positive psychology intervention is feasible (participants will complete 5 out of 8 phone sessions) and acceptable in HSCT patients.

**Specific Aim #2 (Effects on psychological outcomes):** To assess whether this preliminary intervention appears to result in improvement in positive affect and other psychological well-being factors as measured by dispositional optimism, anxiety, and depression.

**Specific Aim #3 (Effects on other outcomes):** To examine the impact of the intervention on overall function and health-related quality of life.

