### *1.3 Hypothesis*

**Hypothesis #1:** The PP exercises will be feasible (i.e., 5 of the 8 phone sessions will be completed by a majority of patients) and acceptable (mean score of at least 6 out of 10 on ratings of ease of completion and subjective utility of the exercises). Furthermore, we will obtain complete objective follow-up data in at least 80% of enrolled participants at the end of the intervention.

**Hypothesis #2:** The intervention will lead to improvements in positive affect and other psychological well-being factors as measured by dispositional optimism, anxiety, and depression at completion compared to baseline.

**Hypothesis #3:** The intervention will lead to improvements in health-related quality of life and functional outcomes at completion compared to baseline.

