## 8.0 Study Endpoints\*

Primary Endpoint: Establishing the positive psychology intervention feasibility and acceptability in HSCT patients will be the primary endpoint.

Secondary Endpoint: Assessing the immediate impact of the PP intervention on participants' positive psychological state and psychological well-being (as measured by dispositional optimism, positive affect, anxiety and depression, adherence and functional outcomes) will be the secondary endpoint.

There are currently no anticipated primary or secondary safety endpoints.

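### Section 11.1 assigns the paired baseline-to-follow-up comparison to Aim 3 only, so Hypothesis 2 (positive affect, optimism, anxiety, depression) has no change analysis as written

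*Combined protocol and SAP*

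**What the plan says.** Section 1.2 separates three aims: feasibility and acceptability (Aim 1), psychological outcomes (Aim 2), and other outcomes (Aim 3). Aim 3 is worded "To examine the impact of the intervention on overall function and health-related quality of life".

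Section 1.3 makes Hypotheses 2 and 3 both contrasts over time. Hypothesis 2 expects improvement in positive affect and in other well-being factors "as measured by dispositional optimism, anxiety, and depression at completion compared to baseline". Hypothesis 3 reads "The intervention will lead to improvements in health-related quality of life and functional outcomes at completion compared to baseline".

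Section 8.0 defines the secondary endpoint as "Assessing the immediate impact of the PP intervention on participants' positive psychological state and psychological well-being", and names optimism, positive affect, anxiety and depression among its components.

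Section 11.1 then allocates the analyses. For the first two aims: "For Aims 1 and 2 (feasibility, acceptability, and immediate impact), descriptive statistics will be used to report proportion of phone session completion", plus mean exercise ratings. For the third: "To compare mean scores on outcome variables for Aim 3, paired t tests will be used", comparing baseline with follow-up. Next come the two-sided .05 threshold, "considered significant, though this study will not be powered to detect statistically significant differences between baseline and follow-up points", and a sentence saying that "we will also consider alternatives to a t-test such as non-parametric tests, effect size calculations". Neither of these last two statements names an aim.

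**The concern.** The two outputs that Section 11.1 gives Aim 2 (sessions completed and exercise ratings) measure feasibility and acceptability, which is Aim 1. Neither measures change in positive affect, optimism, anxiety or depression. The analysis that would address Hypothesis 2 is attached to an aim that does not contain those outcomes.

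If the plan is followed literally, the trial collects paired data for a stated hypothesis and never analyses them. If the investigators run the tests anyway, the choice of test, of baseline and of how to read significance is unplanned for these scores. A later reader could not tell planned from post hoc results. At stake is the psychological part of the secondary endpoint, including optimism and positive affect, which Section 2.3 gives as its examples of outcomes of interest.

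**Working it through.** The plan states no power or effect size for these outcomes, so there is no figure to reproduce. The check sets the sections side by side and then counts scores.

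**Step 1. What each aim needs and what it is given**

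| Aim | Outcomes (1.2, 1.3) | Contrast (1.3) | Analysis (11.1) |
|---|---|---|---|
| 1 | Session completion, ease and utility ratings | None over time | Descriptive: completion, mean ratings |
| 2 | Positive affect, optimism, anxiety, depression | Completion vs baseline | Same descriptive outputs as Aim 1 |
| 3 | Function, health-related quality of life | Completion vs baseline | Paired t tests |

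The Aim 2 row does not match. Section 11.2 only disclaims power, and no other section analyses change in PANAS, LOT-R or HADS.

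**Step 2. Are the data there?** Yes. Section 9.2 has PANAS, LOT-R and HADS completed at the pre-intervention visit and repeated at the follow-up session, and the schedule in Section 7.1 agrees.

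**Step 3. Could the exercise ratings stand in for Aim 2?** No. In Section 9.2 the per-session items are 10-point ratings of ease, utility, happiness and optimism (Section 9.1 refers to positive affect). They are not the validated instruments, do not cover anxiety or depression, and are not a completion-versus-baseline contrast.

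**Step 4. Count the scores**, using the measures listed in Section 9.3.

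- Aim 2: PANAS positive affect, LOT-R, HADS anxiety, HADS depression = 4.
- Aim 3: FACT-BMT (assumed to be one total score), PROMIS-PF-20, PROMIS-Fatigue-8a (assumed to be a functional outcome) = 3.
- Without an assigned change analysis: 4 of 4 + 3 = 7. If fatigue is outside Aim 3, 4 + 1 = 5 of 7.

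**Step 5. What extending the paired tests does to false positives**, with alpha = .05 and no true change.

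- Expected number, k × 0.05: 3 × 0.05 = 0.15; 7 × 0.05 = 0.35.
- Chance of at least one if the scores were independent, 1 − 0.95^k: 1 − 0.95^3 = 0.143; 1 − 0.95^7 = 0.302.
- Upper bound under any dependence, k × 0.05: 15% and 35%.

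**Step 6. What the analysis could show.** With the 10 completers anticipated in Section 11.2, the half-width of a 95% confidence interval for mean change is t(0.975, 9)/√10 = 0.72 standard deviations of the differences. A two-sided paired t test at .05 has power of about 9%, 29% and 62% for standardized changes of 0.2, 0.5 and 0.8 (illustrative values, not from the protocol). This agrees with the protocol's own statement that it is not powered, and it is a reason to report intervals and effect sizes alongside p values.

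**The case against.** The strongest reply is that this is a labelling slip, with the intended analysis visible elsewhere. The three-item list in Section 2.3 ends with exploring benefit on outcomes such as optimism and positive affect. If Section 11.1 was written against that list, its third aim includes the psychological scores. The statements on power and on alternatives to the t test also refer to baseline and follow-up without naming an aim. This makes a slip the likely explanation, but it does not rescue the text. The list is not labelled as aims, Section 1.2 is, and Section 11.1 itself ties immediate impact to Aims 1 and 2.

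Second, the Section 8.0 endpoint does not map cleanly onto Aim 2. It also includes functional outcomes and adherence, and adherence has no instrument in the Section 9.3 list. That is correct, and it is a separate gap which the rewording below does not close.

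Third, the false-positive figures describe the remedy rather than the present defect, and the count of seven depends on splitting HADS and treating FACT-BMT as one score. Both points stand. The figures serve only to show why the new text should say how p values are read.

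Fourth, the minimum repair is to move Aim 2 to the paired-test sentence; confidence intervals, required effect sizes, a named baseline and a note on multiplicity go further. That is fair. They are small additions consistent with the exploratory status in Section 11.2, and the reassignment of Aim 2 is the essential part.

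**Conclusion.** The concern holds. Section 11.1 contradicts Sections 1.2 and 1.3, and as written none of the four Hypothesis 2 outcomes has a baseline-to-follow-up analysis. This is four of seven self-report scores on the counting assumptions above, or five of seven if fatigue falls outside Aim 3. The mismatch itself does not depend on those assumptions.

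The consequence is limited. The study is single-arm and exploratory, the affected aim is secondary, the data will be collected, and the primary aim is untouched. It should be fixed because it is an error in the only analysis plan and the correction is cheap.

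**What to change.** Reword Section 11.1 along these lines:

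> Aim 1: phone session completion (as a proportion) and mean exercise ratings will be summarised descriptively. Aims 2 and 3 (exploratory): scores at the pre-intervention visit (baseline) and at follow-up will be compared by paired t test for PANAS positive affect, LOT-R, HADS anxiety and HADS depression (Aim 2), and for FACT-BMT, PROMIS-PF-20 and PROMIS-Fatigue-8a (Aim 3). Mean change with 95% CI and an effect size will be reported for each score. Non-parametric paired tests will be considered as an alternative in view of sample size and drop-out. Tests are two-tailed; p values are not adjusted for the seven comparisons, and p < .05 is exploratory and does not confirm Hypothesis 2 or 3.

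The sponsor should confirm the baseline. Sections 20.0 and 27.0 place baseline collection at the outpatient visit before the intervention, but the schedule in Section 7.1 also marks these measures at enrollment.

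The cost is the wording of one section. No visits, instruments or patients are added.

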**7.0 Study Timelines\***

*7.1 Subject Participation in the study*

The planned duration of total participant participation in the intervention is 24 weeks, broken down as follows: at weeks four, eight and twelve following consent and eligibility determination, participants will receive check-in/psychosocial support phone calls about their recovery, then week 14 is for self-assessment questionnaires prior to the 8-session weekly positive psychology treatment, and the last week will be used for a repeat of self-report measures obtained at baseline. Patients will also be given the option to complete self-reported measures via mail vs. phone.

**PROTOCOL TITLE: Development of a positive psychology intervention to improve mood and health related quality of life in patients post hematopoietic stem cell transplantation- Proof of Concept Trial**

Based on prior recent experience with recruitment from this patient population, we anticipate about 6-months for the total number of patients for the study.

We are estimating the study will be completed in June 2019.

	Enrollment	Check-In/Psychosocial support phone calls (weeks, 4, 8, 12)	Pre-Intervention Visit	Week 1 of PP-intervention	Week 2 of PP-intervention	Week 3 of PP-intervention	Week 4 of PP-intervention	Week 5 of PP-intervention	Week 6 of PP-intervention	Week 7 of PP-intervention	Week 8 of PP-intervention	Follow-Up Session
HSCT team meeting review to confirm eligibility	X											
Assessment of inclusion criteria	X											
Obtain Consent	X											
10-min phone call		X										
PP exercise				X	X	X	X	X	X	X	X	
Follow-up session												X
Self-report measures (LOT-R, PANAS, HADS, PROMIS-PF-20, PROMIS-Fatigue-8a, FACT-BMT)	X		X									X

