## 9.0 Procedures Involved\*

### 9.1 Study Design

**PROTOCOL TITLE: Development of a positive psychology intervention to improve mood and health related quality of life in patients post hematopoietic stem cell transplantation- Proof of Concept Trial**

The goals of this study are to assess the feasibility, acceptability and preliminary impact of this novel 8-session weekly PP-based intervention for HSCT patients.

Patients will be approached close to their discharge from the hospital after their HSCT for eligibility determination and to obtain consent. After consent is obtained, eligibility will be determined with the mini international neuropsychiatric interview (MINI) and a brief cognitive assessment (with the BIMS) to exclude patients who need more intensive psychological or psychiatric care or have cognitive deficits. Upon agreement and consent to participate in the study, participants will receive check-in/psychosocial support phone calls at weeks four, eight and twelve to provide support and check-in on how their recovery is going since discharge, develop rapport and prepare them for the positive psychology treatment portion of the intervention which will start between Day 90-120 post HSCT. Between the 90-120-day point, when patients return to the clinic for their routine 100-day post HSCT follow-up, the interventionist/principal investigator will meet briefly with the patients in clinic to complete self-assessment questionnaires to measure positive affect, optimism, anxiety, depression, HSCT-specific health related quality of life, adherence and overall function. For the rare situations when participants cannot complete these self-assessment questionnaires in person, patients will be given the option to complete self-assessment questionnaires by phone or mail.

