**13.0 Withdrawal of Subjects\***

We do not anticipate any circumstances under which the subjects will be withdrawn from the research without their consent. We do not anticipate any termination of patients. When informed consent is being obtained from patients, we will emphasize to patients that they can withdraw from the study at any time for any discomforts. Subjects who withdraw from the study will still have their data potentially analyzed depending on when in the study they withdraw and patients will be informed of this as well. We will ensure that contact with participants is confidential by using only the phone numbers and other contact information that are specifically allowed by the participants and not leaving study-related messages for participants unless expressly allowed by participants. Upon enrollment, we ask all participants if it is acceptable to leave voice messages on their phones, as well as the appropriate times to call them. We adhere to any and all patient requests regarding contact.

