**23.0 Local Number of Subjects**

The plan is to accrue 25 subjects locally. We are expecting to enroll about 25 patients with an anticipated number of completers to be 10.

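### Does the session-completion criterion for feasibility need its denominator and unit written into section 11.1?

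*Combined protocol and SAP*

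**What the plan says.** Section 1.3 sets the session part of the feasibility criterion: "5 of the 8 phone sessions will be completed by a majority of patients". Aim 1 in section 1.2 puts it as "participants will complete 5 out of 8 phone sessions". Neither says which patients form the base. The next sentence of Hypothesis 1, on follow-up data, does name one: "we will obtain complete objective follow-up data in at least 80% of enrolled participants at the end of the intervention".

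Section 11.1 is the only analysis text for this criterion. It plans that "descriptive statistics will be used to report proportion of phone session completion and mean scores on exercise ratings" and gives no unit or base.

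On who is enrolled, section 9.1 says "After consent is obtained, eligibility will be determined with the mini international neuropsychiatric interview", and section 7.1 times the check-in calls "at weeks four, eight and twelve following consent and eligibility determination". Enrolment therefore precedes the first session, which section 9.1 places at Day 90-120 after transplant. Section 27.0 notes that patients may change their minds in that interval, and section 19.0 has consent reaffirmed before the questionnaires.

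On withdrawals, section 13.0 says "Subjects who withdraw from the study will still have their data potentially analyzed depending on when in the study they withdraw". On numbers, section 23.0 says "We are expecting to enroll about 25 patients with an anticipated number of completers to be 10", and section 11.2 repeats both figures.

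**The concern.** Feasibility is the primary aim, and this part of it has a numeric pass mark. Consent is taken during the transplant admission and the sessions begin about three months later, so some loss before session 1 is foreseeable. Section 2.3 reports that early post-transplant burden varies widely and may make participation hard. If people lost in that interval could be dropped from the base, the same data could pass or fail depending on a choice made after they are seen. The wording in section 11.1 also allows a session-level percentage, which does not answer a criterion about people. Section 13.0 could be read as letting early leavers fall out of the count. A favourable figure obtained in any of these ways would be carried into the larger pilot.

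**Working it through.** **Inputs.** 25 enrolled and 10 anticipated completers (sections 11.2 and 23.0); at least 5 of 8 sessions by a majority (section 1.3). I take a majority as more than half. The plan gives no calculation for this criterion, so there is no derived figure to reproduce.

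**Assumption.** The 10 completers are exactly those who reach 5 sessions. Someone could reach 5 and miss follow-up, so the count could exceed 10; the range below allows for this.

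**1. Effect of the base.** Over all enrolled, a majority needs more than 12.5, so at least 13 of 25.
- 10/25 = 40% (exact 95% CI 21% to 61%): not met.
- 10/20 = 50%: not met.
- 10/19 = 52.6% (exact 95% CI 29% to 76%): met.

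The result turns when the base falls to 19, that is, when 25 − 19 = 6 of the 15 others are left out. In general, x people are a majority of n when n ≤ 2x − 1, so the number to leave out is 25 − (2x − 1) = 26 − 2x.

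| Reach 5 sessions (x) | x/25 | Others left out before it turns | Proportion then |
|---|---|---|---|
| 8 | 32% | 10 of 17 | 8/15 = 53% |
| 9 | 36% | 8 of 16 | 9/17 = 53% |
| 10 | 40% | 6 of 15 | 10/19 = 53% |
| 11 | 44% | 4 of 14 | 11/21 = 52% |
| 12 | 48% | 2 of 13 | 12/23 = 52% |
| 13 or more | 52% or more | none needed | met on either base |

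The documents do not split the expected loss into before and after session 1, so they do not show that these numbers would be reached.

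**2. Which base the text supports.** Sections 4.0, 11.2 and 23.0 all use the word patients for the 25. The follow-up sentence, which continues Hypothesis 1, refers to enrolled participants. Section 7.1 counts 24 weeks of participation in the intervention from consent, with the check-in calls included. No section defines a population of people who started session 1. The natural base is the 25 enrolled.

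**3. Which unit the text supports.** Section 1.3 sets the criterion per patient. The follow-up text in section 9.2 likewise applies its rule of at least 5 sessions to each participant. A session-level figure could not stand in for this. With 25 × 8 = 200 sessions, 12 people doing 8 and 13 doing 4 gives (96 + 52)/200 = 74% of sessions but 12/25 = 48% of people. Anyone judging Hypothesis 1 must therefore count people, and the same session records supply that count.

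**4. Withdrawals.** Section 13.0 concerns the use of data from people who leave. It removes no one from the feasibility count. Whether a person reached 5 sessions is known from the session record, without analysing any questionnaire.

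**The case for a change.** The strongest opposing case is that a primary criterion with a threshold should not depend on a natural reading. The authors named a base for the follow-up part and not for the session part, and section 9.2 cites earlier studies by their completion rate of exercises, so a session-level reading is not far-fetched. The count the protocol expects, 10 of 25, lies within the range where the base matters, and one sentence would settle it.

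Part of this stands. A starters-only figure is not expressly ruled out, and stating the base would be tidy. But the two readings do not have equal support: one matches the protocol's use of its own terms, and the other has to be inferred from the possibility of early loss. The cited completion rate describes earlier work and does not set this trial's criterion. The contrast between 40% and a required majority comes mainly from a separate tension, namely planning for 10 completers while requiring at least 13. Naming the base would not resolve that.

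**Conclusion.** No change is needed. Section 11.1 leaves out a detail that sections 1.3, 4.0, 9.2 and 23.0 allow an analyst to supply: participants with at least 5 of 8 sessions, over all 25 enrolled. No stated rule gives a wrong result.

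The possible effect is limited to 8 to 12 people reaching 5 sessions, with at least 10 to 2 others respectively left out on a base the protocol does not name. At 13 or more the base makes no difference. Even in the central case, the intervals for 10/25 (21% to 61%) and 10/19 (29% to 76%) both include 50%, so neither proportion settles the matter in a study this small. The trial is a non-randomized proof of concept with descriptive feasibility analysis, and no stop-or-go rule is attached to this criterion. A report giving the numbers enrolled, starting and reaching 5 sessions lets a reader form either proportion.

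The figures rest on equating completers with those who reach 5 sessions, and the conclusion rests on reading patients as the 25 enrolled.
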